4.4.7 Data Presentation and Analysis Plan

The primary purpose of this study is to evaluate the safety of this device as there are no or very limited devices and clinical options available for this patient population. The primary safety endpoint of this study is freedom from major adverse events (MAE) at 30 days or during hospitalization if this exceeds 30 days. Major adverse events include death, bowel ischemia, myocardial infarction, paraplegia, renal failure, respiratory failure, and stroke. The primary safety endpoint will be analyzed to determine statistical significance when compared to a target performance goal. A literature review of outcomes of open surgical repair was used to create the performance goal as there is not a comparable endovascular option to use for analysis. The performance goal was selected based on the range of subjects experiencing a major adverse event at 30 days. The range was calculated based on assumptions of the minimum and maximum number of subjects experiencing at least one MAE in the historical open surgical repair group (Table 6). Based on the literature reviewed and the above assumptions the range of subjects experiencing at least one MAE in the open surgical repair group is 30.5% to 77.4%.

The primary effectiveness endpoint is the proportion of the study subjects with treatment success at 1 year. The data will be presented as quality outcomes, with the number of study subjects who experience treatment success compared to the overall patient population.

Additionally, data outcomes from this study will be entered into a common vascular database so that data can be pooled with other PS-IDEs. This would provide consistent reporting across the PS-IDEs. Additionally, the PS-IDEs will be evaluating the same device and endpoints to allow for a pool-ability of data across the sites.

The data will be separated into two separate study arms: primary study arm and expanded selection arm.

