3.9 Report of Prior Investigations Synopsis

The single center experience with the Visceral Manifold Thoracoabdominal Stent Graft System from Sanford Health ([name]; PS-IDE (G140207) were recently reported.¹ 29 patients were successfully treated between March 2012 and January 2016. Twenty-seven patients were followed up to 1 month, 21 were followed up to 6 months, 16 were followed up to 1 year, and 8 have been followed past 1 year thus far. Using the Crawford classification, there were 8 with a type 1/type 2, 6 type 3, 8 with type 4, and 7 with type 5. 97.3% (108 of 111) of target vessels were successfully stented and 99% (107 of the 108) target vessels remained patent throughout follow-up. 15 patients in this experience met inclusion criteria (identical to ours) and were enrolled in the primary arm and 14 did not meet inclusion criteria and were treated as compassionate use. The majority of this latter group would have been considered part of the expanded arm of our protocol. Specifically, 4 were emergency ruptures, 5 were chronic type B dissections, and the remaining 5 had suprarenal fixated stents or an occluded renal (total n=14). In the group meeting IDE inclusion criteria, there was an average length of stay of 7.5 days with no in-hospital or 30-day death, no cases of paraplegia, and one case of renal failure which resolved. There was one death at 11 months from a CVA. In the group not meeting IDE inclusion criteria, there was an average length of stay of 9.5 days, with no in hospital or 30-day death, two cases of paraplegia, and six cases of temporary or permanent renal failure.

When contrasted with open repair's significant complication rates and branch fenestrated device's significant anatomic and logistic limitations, the potential risk of the proposed novel graft does not outweigh the potential benefit of widened anatomic availability and improved patency rates. Given the potential benefits, we feel that it is justified to expose the target patient population to the potential risk. The non-clinical testing performed by Medtronic and the clinical results reported by Sanford Health show adequate safety of the device to support a clinical study.

4. Investigation Plan

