4.4.3 Study Endpoints

The primary safety endpoint is freedom from major adverse events (MAE) at 30 days or during hospitalization if this exceeds 30 days.

Major adverse events include death, bowel ischemia, myocardial infarction, paraplegia, renal failure, respiratory failure, and stroke.

The primary effectiveness endpoint is the proportion of the study subjects with treatment success at 1 year. Treatment success is defined as a composite of technical success and freedom from the following:

- Aneurysm enlargement i.e., $\geq 5\text{mm}$ as compared to any previous CT measure using orthogonal (i.e., perpendicular to the centerline) measurements
- Aneurysm rupture
- Aneurysm-related mortality
- Conversion to open repair
- Secondary intervention for migration, Type I and III endoleaks, device integrity failure (e.g., fracture), and patency-related events (i.e., device component stenosis or occlusion and embolic events)

Secondary endpoints include:

- Technical success and the individual components of technical success:
 - Successful delivery
 - Deployment at the intended implantation site
 - Patency of all endovascular graft and stent components
 - Absence of device deformations requiring unplanned placement of an additional device
 - Absence of inadvertent covering of aortic branch vessels
 - Successful withdrawal
- Freedom from the individual components of the primary safety endpoint at 30 days:
 - Death
 - Bowel ischemia
 - Myocardial infarction
 - Paraplegia
 - Renal failure
 - Respiratory failure
 - Stroke
- Freedom from paraparesis at 30 days
- The following at each follow-up interval:
 - Treatment success and the individual components of treatment success including freedom from the following:
 - Aneurysm enlargement
 - Aneurysm-related mortality

- Aneurysm rupture
- Conversion to open repair
- Secondary intervention for migration, type I and III endoleaks, device integrity failure (i.e., fracture), and patency-related events (i.e., device stenosis or occlusion and embolic events).
- Renal failure
- All-cause mortality
- Endoleaks
- Device integrity failure (e.g., fracture)
- Patency-related events (i.e., device stenosis or occlusion and embolic events)
- Other device-related events

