4.4.4 Follow-up Schedule

Patients included in the study will undergo follow-up at one month, six months, twelve months and then annually for five years. In the event of patient death, an autopsy may be performed.

Table 5. Follow-up Table

	Pre- op	Intra- op	Pre- discharge	Month						
				1	6	12	24	36	48	60
CTA/CT Scan with and without	X		X ⁸	X ²						
X-Ray	X ¹			X ¹						
Angiography	X ³	X								
Blood Tests	X ⁴	X ^{5, 6}	X ⁴							
Clinical Exam (including ABI)	X ⁷		X	X ⁷						
Branch Patency ² (duplex ultrasound)				X	X	X	X	X	X	X

- 1 Device X-ray may be requested to provide more focused imaging if potential device integrity issues are identified, but are unable to be confirmed, using CT. Per standard of care: A/P, Lateral and Bilateral oblique views.
- 2 In patients experiencing renal failure during follow-up, duplex ultrasound may be used in conjunction with non-contrast CT.
- 3 Pre-procedure angiography may be requested at discretion of film reviewer.
- 4 Blood tests include hemoglobin and creatinine; PTT and prothrombin collected pre-op and pre- discharge only.
- 5 Blood test for ACT.
- 6 Other intra-op labs for anesthesia.
- 7 Urine pregnancy test (for female patients of childbearing age)
- 8 If deemed necessary by the Principal Investigator

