4.4.5.6 Follow-up Visits

All patients will undergo follow-up at one month, six months, twelve months and then annually for five years (as described in Section 1.4.4). At each of the follow-up visits the following tests will be performed:

- Physical examination
- Complete blood count to evaluate white blood cells, hemoglobin, and platelets
- Basic metabolic panel to evaluate creatinine
- Pregnancy test (for female patients of child bearing age)
- CTA of the chest, abdomen, and pelvis if renal function allows
- If deemed necessary by the investigator, an X-Ray may be performed if potential device integrity issues are identified but unable to be confirmed by CT. This will be done per local standard of care with A/P, Lateral and Bilateral Oblique Images obtained.

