4.9 Definitions

Aortic aneurysm enlargement: $\geq 5\text{mm}$ as compared to any previous CT measure using orthogonal (i.e., perpendicular to the centerline) measurements

Aortoiliac aneurysm: aneurysm of the abdominal aorta and including one or both of the iliac arteries

Aneurysm-related mortality:

Death occurring within 30 days or during hospitalization following the index procedure, unless there is evidence of accidental or self-inflicted death;

Death occurring within 30 days or during hospitalization following conversion to open repair or a secondary intervention for migration, Type I and III endoleaks, device integrity failure (e.g., fracture), or patency-related events (i.e., device stenosis or occlusion and embolic events), unless there is evidence of accidental or self-inflicted death;

Death occurring within 30 days or during hospitalization for a complication of the aneurysm or a complication associated with the device, such as:

- aortic rupture
- fistula formation (e.g., aorto-enteric)
- embolization
- malperfusion of organ(s) or limb(s)

Arterial fistula formation: formation of an abnormal connection or passageway between an artery and adjacent structures

Conversion to Open, Early: any open repair within 30 days of the index procedure involving the vasculature in the abdomen and/or pelvis.

Conversion to Open, Late: any open surgical repair involving stentgraft removal after 30 days post index procedure

Chronic Obstructive Pulmonary Disease (COPD): forced expiratory volume (FEV1) < 1.0 liter or receiving home oxygen

Crawford Type IV TAAA: aneurysmal dilatation originating within 5cm of the celiac artery

Disabling stroke: Modified Rankin Score MRS >2

Distal landing zone: aortic fixation site furthest from the heart

Embolization: dislodging of an upstream particle that travels downstream causing blockage of free flow further downstream. Embolization could result in malperfusion

Embolus: blood clot that forms at one location (presumably from the aneurysmal sac, aortic neck, or adjacent vessels) and is dislodged to another location resulting in ischemic changes

Emergent: an aneurysm requiring immediate treatment

Endoleak:

Type I: leak occurring at the proximal or distal fixation site, including leakage around fenestrations

Type Ia: leak occurring at the proximal fixation zone of the stent-graft

Type Ib: leak occurring at the distal fixation zone of the stent graft

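### The plan does not settle how late unrelated deaths, losses and absent 12-month CTs enter the 1-year treatment-success proportion, and its wording permits counting them as successes

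*Combined protocol and SAP*

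**What the plan says.** Section 4.4.7 states: "The primary effectiveness endpoint is the proportion of the study subjects with treatment success at 1 year". The result is to be presented "with the number of study subjects who experience treatment success compared to the overall patient population". No performance goal, hypothesis, expected rate or power is attached to it.

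Section 4.4.3 gives the definition: "Treatment success is defined as a composite of technical success and freedom from the following". The list contains enlargement of 5 mm or more against any previous CT, rupture, "Aneurysm-related mortality", conversion to open repair, and secondary intervention for specified causes. All-cause mortality appears only among the secondary endpoints.

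Section 4.9 defines which deaths count as aneurysm-related. The first category is "Death occurring within 30 days or during hospitalization following the index procedure, unless there is evidence of accidental or self-inflicted death". The others are deaths after conversion or a listed secondary intervention, and deaths from a complication of the aneurysm or device.

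On imaging, section 4.4.5.6 provides at each visit for "CTA of the chest, abdomen, and pelvis if renal function allows". Table 5, footnote 2, in section 4.4.4 adds: "In patients experiencing renal failure during follow-up, duplex ultrasound may be used in conjunction with non-contrast CT". The expanded arm (section 4.4.2) admits subjects with baseline creatinine above 2.0 mg/dL.

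Section 4.1 describes the effectiveness aim as the proportion who reach treatment success and keep it at one year. Table 8 in section 4.7 counts deaths, losses and adequate imaging by visit, but for the annual progress report.

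**The concern.** A composite built as the absence of listed events needs a rule for subjects in whom the events can no longer occur or were not looked for. This plan has none. Three kinds of subject are affected: those who die of an unrelated cause after the early period, those lost before 12 months, and those with no 12-month diameter on which enlargement could be judged. Read literally, the list records no failure for any of them, and the denominator keeps them in.

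With 6 and 9 subjects per arm, the treatment of a single subject changes the reported figure visibly. The expanded arm takes ruptures, failure of two major organ systems and raised creatinine, so the question is a practical one there. The data are to be pooled with other physician-sponsored studies and used to plan a pivotal study (sections 4.4.6 and 4.4.7). An unwritten rule could be applied differently from site to site.

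**Working it through.** **No figure to reproduce.** The documents state no expected 1-year success rate, so the check is of how far the unstated rule can move the result.

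**Inputs.** Arm sizes 6 and 9, total 15 (section 4.4). The rate of late unrelated death, loss or absent 12-month CT is not given. I assume 0 to 4 undetermined subjects among 15.

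**Notation.** N is the number of subjects and f the number with an observed failure. The number undetermined is m: technical success and no observed listed failure, but an unrelated death, a loss or no 12-month CT diameter before 1 year can be assessed.

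- Counted as success: (N − f)/N
- Counted as non-success: (N − f − m)/N
- Left out: (N − f − m)/(N − m)

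**Effect of one subject.** The first two differ by m/N. For m = 1 this is 1/6 = 16.7 points, 1/9 = 11.1 points and 1/15 = 6.7 points.

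**Illustration** with assumed failures of 1 in 6, 2 in 9 and hence 3 in 15:

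| N | f | m | Counted as success | Counted as non-success | Left out |
|---|---|---|---|---|---|
| 6 | 1 | 1 | 5/6 = 83.3% | 4/6 = 66.7% | 4/5 = 80.0% |
| 9 | 2 | 1 | 7/9 = 77.8% | 6/9 = 66.7% | 6/8 = 75.0% |
| 15 | 3 | 0 | 12/15 = 80.0% | 12/15 = 80.0% | 12/15 = 80.0% |
| 15 | 3 | 1 | 12/15 = 80.0% | 11/15 = 73.3% | 11/14 = 78.6% |
| 15 | 3 | 2 | 12/15 = 80.0% | 10/15 = 66.7% | 10/13 = 76.9% |
| 15 | 3 | 3 | 12/15 = 80.0% | 9/15 = 60.0% | 9/12 = 75.0% |
| 15 | 3 | 4 | 12/15 = 80.0% | 8/15 = 53.3% | 8/11 = 72.7% |

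The last column departs from the overall-population denominator in section 4.4.7. The first two rules both fit the text.

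**A case of this kind in the plan.** Section 3.9 reports, among 15 earlier subjects who met the criteria: "There was one death at 11 months from a CVA". Suppose that death was not aneurysm-related, and suppose for illustration that all 15 were otherwise followed to 1 year without failure. Success is then 15/15 = 100%, 14/15 = 93.3% or 14/14 = 100% under the three rules.

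**Imaging route.** Section 4.9 defines renal failure as the need for dialysis or hemofiltration. A subject enrolled with creatinine above 2.0 mg/dL who never reaches that point is not covered by the words of footnote 2, while section 4.4.5.6 makes the CTA conditional on renal function. The two places do not together name a route to a diameter for that subject, though neither forbids one.

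**The case against.** The strongest reply is that no sentence tells the analyst to count these subjects as successes. A subject who died at month 3 has not plainly maintained success at one year in the sense of section 4.1, and a whole-population denominator fits the conservative count at least as well. This stands. A reader might infer that the plan prescribes the lenient count and that the reported rate is therefore biased upward. The documents support only that the wording permits it.

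A reader might also infer that missing scans are likely. That is not supported either. The Table 5 row covers CT with and without contrast as well as CTA, enlargement is measured on CT and not specifically on CTA, and non-contrast CT is nowhere prohibited. Nor does the earlier experience help. Section 3.9 has 16 of 29 subjects followed to one year, but treatment ran from March 2012 to January 2016 and some were not yet due, so this says nothing about loss or absent imaging.

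In the secondary-endpoint lists, all-cause mortality appears beneath the components of treatment success. The list levels may have been lost in reading the PDF. The primary-endpoint list and the definition in section 4.9 name only aneurysm-related mortality, so this does not close the gap.

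Finally, the endpoint is descriptive, safety is the stated main purpose, and all-cause mortality is reported at each interval. That limits the consequence, because unrelated deaths would be visible beside the success rate. It does not settle which success rate is reported.

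**Conclusion.** The point holds as a gap in the endpoint rule: two counts are compatible with the text and the plan does not choose between them. If undetermined subjects are counted as free from failure, effectiveness is overstated by m/N relative to the conservative count, which is 16.7, 11.1 or 6.7 points per subject for n = 6, 9 or 15. The total depends on m, which the documents do not give; 0 to 4 is an assumption.

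The case for unrelated deaths is the firmer part, since they lie outside the listed failures by definition. An absent CT leaves enlargement unknown and does not establish its absence. This should be corrected before the 1-year data are analyzed. It does not affect the 30-day safety endpoint.

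**What to change.** - In section 4.4.7, state that a 1-year success is a subject alive at 12 months with technical success, an adequate 12-month CT (contrast or non-contrast) and no listed failure event, over all subjects in the arm.
- Report by arm the number evaluable and the numbers of unrelated deaths, losses and absent CTs. Give a best-case proportion (all undetermined subjects counted as successes) and a worst-case one (all counted as failures). With the full denominator the headline equals the worst case, so the best case must stand beside it: an absent scan is not evidence of failure, and the strict count may understate success in subjects with poor renal function.
- Show the proportion under the common definition of the pooled studies alongside, so that poolability is kept.
- Label any Kaplan-Meier freedom from treatment failure, with unrelated death and loss censored at the last adequate imaging, as supportive. It treats unrelated death differently from the proportion, and it is imprecise at these sizes.
- Reconcile Table 5, footnote 2, with section 4.4.5.6 on imaging for subjects with raised baseline creatinine.
- Fix which failure list applies: the treatment-success entry in section 4.9 uses 10 mm for enlargement and adds renal failure, unlike section 4.4.3.

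The cost is a few sentences and one extra table, mostly from counts that Table 8 already collects. The stated success rate may fall slightly.

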4.4.7.1 Statistical Methods

The primary hypothesis of the Visceral Manifold Study is the number of subjects experiencing a major adverse event through 30 days will be less than a target performance goal (PG) of 50%. The PG was determined by using a conservative target that is approximately the average of the open surgical repair MAE rate calculated above (30.5%-77.4%, Table 6). The anticipated test device 30 day MAE rate was based on the current rate of MAE's (26%, Table 7) observed in 20 subjects meeting inclusion criteria into the primary study as of June 2016.

The sample size for the Visceral Manifold Study was determined using an exact method based on a one-sided 2.5% significance level and an anticipated 26% investigational device 30 day major adverse event rate. Based on these assumptions, a sample size from the pooled PS-IDE data of 46 subjects provides at least 80% power to test the primary hypothesis.

Table 6. Historical Comparison for Primary Safety Endpoint (MAE Rate at 30 days for Open Repair)

Reference	# of Patients	Mortality	Bowel Ischemia	Myocardial Infarction	Paraplegia	Renal Failure	Respiratory Failure	Stroke
Rigberg et al	1010	191 (19%)						
Becquemin et al	1678	90 (5.4%)	51 (3%)	20 (1.2%)	16 (1%)	289 (17.2%)	124 (7.4%)	12 (0.7%)
Murana et al	542	46 (8.5%)			22 (4.2%)			
Ferrer et al	257	16 (6.2%)			53 (20.8%)	31 (12.3%)	31 (12.3%)	
Bensley et al	450	45 (10%)		10 (2.4%)		48 (10.7%)	202 (45.1%)	9 (2.2%)
Nathan et al	83	6 (5.6%)						
Dayama et al	682	68 (10%)		87 (12.9%)		117 (17.2%)	286 (42%)	

Ferrante et al	200	5 (2.5%)		25 (12.8%)		22 (11%)	27 (13.8%)	
Tsiliimparis et al	1091	58 (5.4%)		87 (8%)		109 (10%)	229 (21%)	
Piazza et al	7833	1331 (17%)			587 (7.5%)	1488 (19%)	2819 (36%)	
Total	13826	1855/13826	51/1678	229/4101	678/10310	2104/12191	3718/12191	21/2128
Rate of MAE at 30 Days for Open Surgical Repair		13.4%	3.0%	5.6%	6.6%	17.3%	30.5%	1.0%

Table 7. Historical Comparison for Expected Investigational Device 30 Day MAE Rate (Outcomes of subjects treated with the Visceral Manifold System and meeting inclusion into the primary study as of June 2016)

Dataset	Mortality	Bowel Ischemia	Myocardial Infarction	Paraplegia	Renal Failure	Respiratory Failure	Stroke
Subjects meeting VMS PS-IDE I/E criteria	0/20 (0%)	0/20 (0%)	0/20 (0%)	2/20 (9.5%)	1/20 (5%)	3/20 (14%)	0/20 (0%)

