A retrospective study reported by Sanford Health (IDE Application G140207, Clinical Use Summary) reports the only subjects that would not be ideal candidates include subjects with prior suprarenal fixation stents, dissection, present emergently. The retrospective study examines 12 patients which meet the clinical study criteria that were treated between 2012 and 2014. In this patient population, there was one subject with renal failure and one subject with a respiratory event in the first 30 days. There was one unrelated patient death and one CVA in the first year. Additionally, in this study there was one instance of branch vessel occlusion and secondary intervention.

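### The 26% planning MAE rate cannot have been observed in 20 subjects, and two Table 7 percentages disagree with their counts

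*Combined protocol and SAP*

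**What the plan says.** Section 4.4.7.1 sets the primary hypothesis that the number of subjects with a major adverse event (MAE) through 30 days "will be less than a target performance goal (PG) of 50"%. As the source of its anticipated device rate it names "the current rate of MAE's (26%, Table 7) observed in 20 subjects meeting inclusion criteria into the primary study as of June 2016". Its power calculation used an "exact method based on a one-sided 2.5% significance level and an anticipated 26% investigational device 30 day major adverse event rate", and concludes that "a sample size from the pooled PS-IDE data of 46 subjects provides at least 80% power to test the primary hypothesis".

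Table 7, the cited source, gives component counts only:

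- paraplegia 2/20, printed as 9.5%
- renal failure 1/20, printed as 5%
- respiratory failure 3/20, printed as 14%
- mortality, bowel ischemia, myocardial infarction and stroke 0/20 each

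It has no entry for subjects with one or more MAEs, although the primary safety endpoint (Section 4.4.3) and the historical comparator (Section 4.4.7) are both defined per subject.

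**The concern.** The 26% is the only device-side input to the power statement, and the plan presents it as an observed rate with a stated denominator. A reader who tries to rebuild it from Table 7 cannot: the fraction does not exist over 20, and the table's own percentages disagree with its counts. What is at stake is whether 46 pooled subjects give the stated power. That depends on how many subjects had at least one MAE, and this count is missing.

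**Working it through.** **1. The plan's power figure on its own input.** Inputs from Section 4.4.7.1: n = 46, null rate 0.50, alternative 0.26, exact one-sided 2.5% test. The cut-off is the largest c with P(X ≤ c | 46, 0.50) ≤ 0.025.

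- P(X ≤ 15 | 46, 0.50) = 0.0129 and P(X ≤ 16 | 46, 0.50) = 0.0270, so the test passes with 15 or fewer MAE subjects (attained alpha 1.29%).
- Power = P(X ≤ 15 | 46, 0.26) = 0.881. The claim of at least 80% is true at 26%.
- At 26%, 80% power first occurs at n = 35 (82.4%), slips to 79.5% at n = 36, and holds from n = 37. So 46 is larger than 26% requires.

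**2. The 26% itself.** 0.26 × 20 = 5.2 subjects. The neighbouring whole counts give 5/20 = 25% and 6/20 = 30%. The printed component percentages do not add to it either: 9.5 + 5 + 14 = 28.5.

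**3. The Table 7 percentages.** 2/20 = 10.0% (printed 9.5%), 3/20 = 15.0% (printed 14%) and 1/20 = 5.0% (printed 5%, correct).

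**4. Would another denominator repair it?** Among denominators 15 to 30, a whole count rounds to 26% only as 5/19, 6/23 or 7/27. Two events give 9.5% only over 21.

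| Denominator | 2 events (printed 9.5%) | 1 event (printed 5%) | 3 events (printed 14%) | Nearest to 26% |
|---|---|---|---|---|
| 19 | 10.5% | 5.3% | 15.8% | 5/19 = 26.3% |
| 20 | 10.0% | 5.0% | 15.0% | 5/20 = 25.0%, 6/20 = 30.0% |
| 21 | 9.5% | 4.8% | 14.3% | 5/21 = 23.8%, 6/21 = 28.6% |
| 23 | 8.7% | 4.3% | 13.0% | 6/23 = 26.1% |
| 27 | 7.4% | 3.7% | 11.1% | 7/27 = 25.9% |

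A denominator of 21 fits all three component percentages but not 26%. The denominators that fit 26% do not fit 9.5%. The true denominator cannot be settled from the text.

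**5. What the printed counts allow.** The number of subjects with at least one MAE is no smaller than the largest component (3) and no larger than the sum (2 + 1 + 3 = 6). The observed rate therefore lies between 3/20 = 15% and 6/20 = 30%.

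**6. Do the other device summaries supply the count?** No. The retrospective summary under Section 3.4.2 covers 12 patients and reports that "there was one subject with renal failure and one subject with a respiratory event in the first 30 days". It does not say whether these were the only subjects with any MAE component. Section 3.9 reports, for 15 subjects meeting the inclusion criteria, "no in-hospital or 30-day death, no cases of paraplegia, and one case of renal failure which resolved", and gives no per-subject MAE total. Table 7 shows two paraplegia events among 20. The cohorts may differ, so this is not in itself a contradiction.

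**7. Power of 46 subjects across the possible rates**, P(X ≤ 15 | 46, p):

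| Rate | Power |
|---|---|
| 3/20 = 15% | 99.9% |
| 4/20 = 20% | 98.6% |
| 5/20 = 25% | 91.0% |
| 26% (plan) | 88.1% |
| 28.2% | 80% (crossing point) |
| 6/21 = 28.6% | 78.2% |
| 6/20 = 30% | 71.3% |

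At 30%, 80% power first occurs at n = 49 and holds from n = 54.

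**The case against.** The strongest reply is that nothing in the design is shown to fail. Of the four subject counts possible over 20, three leave power at 91.0% or more, and the nearest, 5/20, makes 26% slightly conservative. The 46 also exceeds the 35 to 37 that 26% needs, which absorbs a one-point error in the input. The calculation concerns pooled data, while this study's 15 subjects (6 primary, 9 expanded) are justified as a feasibility sample. The text also calls the planning rate anticipated. Finally, Table 7 may contain just one slip, 20 printed for 21; the worst case would then be 6/21, with power 78.2%, less than two points short.

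Most of this stands. It limits the consequence and bears on how the table is corrected. It does not rescue the sentence, which ties 26% to an observation in 20 subjects. A denominator of 21 is an inference the documents do not state, and 26% fails over 21 as well. Pooling is no answer either: this protocol prints the calculation as its own statistical method, and Section 4.4.6 relies on the pooled data to develop a pivotal study.

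**Conclusion.** The point holds: the source given for 26% is wrong as written, and the paraplegia and respiratory failure percentages in Table 7 do not match their counts. The power claim is true at 26%. On the printed counts it fails only if all six component events fell in six different subjects (71.3%), which the documents neither show nor exclude. The 80% crossing, 28.2%, lies only about two points above the planning rate, and any rate from about 20 subjects is imprecise. If the count were 5 of 20, for illustration, the exact 95% interval would run from 8.7% to 49.1%. The power figures assume the exact one-sided 2.5% test against 50% with 46 evaluable subjects. The cut-off, type I error and this trial's enrolment do not change. This should be fixed, because a stated design input cannot be reproduced.

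**What to change.** - Establish the true denominator and make the Table 7 counts and percentages agree with it.
- Replace 26% with the number of subjects with at least one MAE over that denominator. If the count cannot be obtained, call 26% an assumed or derived rate and state the derivation.
- Restate the power of 46 subjects at the resulting rate. Also report the true rate at which power reaches 80% (28.2%), so that readers can see the margin.

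**Cost.** If 20 is right, two table cells change. If 21 is right, the denominators of all seven table entries change, as does the number of subjects in the text. In either case one subject-level count and one power figure are added, with no extra patients. The count may have to come from another PS-IDE sponsor, since Section 3.9 attributes the prior device experience to another institution; relabelling needs no data. The downside is that the restated power may fall below 80%.
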